Abbreviation	Definition
ID	identification
IEC	independent ethics committee
IL	interleukin
IPL	intense pulsed light
IRB	institutional review board
ITT	intent to treat
JAK	Janus kinase
MedDRA	Medical Dictionary for Regulatory Affairs
Nd:YAG	Neodymium-doped yttrium aluminium garnet; Nd:Y ₃ Al ₅ O ₁₂
NRS	numeric rating scale
PGIC	Patient Global Impression of Change
P-gp	P-glycoprotein
PK	pharmacokinetic
QD	once daily
QTcF	QT interval corrected for heart rate using Fridericia's formula
RNA	ribonucleic acid
SAE	serious adverse event
SOP	standard operating procedure
STAT	signal transducer and activator of transcription
TB	tuberculosis
TEAE	treatment-emergent adverse event
Th	T helper cell
TNF-α	tumor necrosis factor alpha
TYK	tyrosine kinase
ULN	upper limit of normal
V _d /F	apparent volume of distribution after non-intravenous administration
WBC	white blood cell

1. PROTOCOL SUMMARY

Protocol Title: A Phase 2, Open-Label, Single-Arm Study of the Safety of INCB054707 in

Participants With Hidradenitis Suppurativa

Protocol Number: INCB 54707-202

Objectives and Endpoints

Table 1 presents the primary and key secondary objectives and endpoints.

Table 1: Primary and Key Secondary Objectives and Endpoints

Objectives	Endpoints				
Primary					
To evaluate the safety and tolerability of INCB054707.	• Frequency, duration, and severity of AEs, clinical laboratory test results, vital signs results, ECGs, and physical examination findings.				
Key Secondary					
To evaluate the systemic exposure to INCB054707.	• Population PK parameters of INCB054707.				
To evaluate the efficacy of INCB054707.	• Proportion of participants with a HiSCR at each visit.				
	 Proportion of participants achieving an AN count of 0 to 2 at each visit. 				
	• Mean change from baseline in the HS Pain NRS scores, worst and average pain, at each visit.				
	 Mean change from baseline to Week 8 in the modified Sartorius scale score. 				
	 Mean change from baseline in the number of draining fistulas count at each visit. 				
	• Proportion of participants at each category of Hurley Stage at baseline and Week 8.				
	 Proportion of participants with change from baseline in Hurley Stage at Week 8. 				
	 Proportions of participants in each HS-PGIC category during the treatment period. 				

Overall Design:

Table 2 presents the key study design elements. Further study details are presented after the table.

 Table 2:
 Key Study Design Elements

Study Phase	Phase 2
Clinical Indication	HS
Population	Men and women aged 18 to 75 years with moderate to severe HS for at least 6 months
Number of Participants	Approximately 10 participants are expected to be enrolled.
Study Design	Multicenter, open-label, and single-arm
Estimated Duration of Study Participation	Up to 28 days for screening, an 8-week open-label, single-arm treatment period, and a 4-week safety follow-up period. The estimated total duration of study participation is approximately 16 weeks for each participant.
Data Safety Monitoring Board	No

Treatment Groups and Duration:

The study design is shown in Figure 1. The schedule of assessments is detailed in Table 3.

Table 3: Schedule of Assessments

		Screening	Treatment				Follow-Up		
Evaluation	Section	Day -28 to -1	Day 1 ^a	Wk 1 ± 1 day	Wk 2 ± 3 days	Wk 4 ^a ± 3 days	Wk 6 ± 3 days	Wk 8a ± 3 days (EOT)	Wk 12 + 7 days (EOS)
Administrative/screening procedures									
Informed consent	8.1.1	X							
Demography/medical history	8.1.4	X							
Inclusion/exclusion criteria	5	X	X						
Prior/concomitant medications	6.6	X	X	X	X	X	X	X	X
Serology	8.3.5.2	X							
Urinalysis	8.3.5.2	X							
TB screening	8.3.5.2	X							
FSH ^b	8.3.5.2	X							
Pregnancy test ^c	8.3.5.3	X	X	X	X	X	X	X	X
Dispense study drug	6.1		X			X			
Distribute reminder cards	8.1.3	X	X	X	X	X	X	X	
Distribute diary	8.1.3	X	X	X	X	X	X	X	
Collect study drug and assess compliance	6.4			X	X	X	X	X	
Safety procedures/assessments	1	.		•					•
Comprehensive physical examination	8.3.2	X						X	
Targeted physical examination	8.3.2		X	X	X	X	X		X
Vital signs	8.3.3	X	X	X	X	X	X	X	X
Hematology and chemistry assessments	8.3.5.1, 8.6	X	X	X	X	X	X	X	X
Lipid panel	8.3.5.1		X					X	
CRP	8.3.5.1		X					X	
12-lead ECG (screening) ^a	8.3.4	X							
12-lead ECG (predose and postdose) ^d	8.3.4		X						
12-lead ECG (postdose only)d	8.3.4				X		X		
12-lead ECG (predose only) ^d	8.3.4							X	
Assess AEs	8.3.1, 9	X	X	X	X	X	X	X	X
Efficacy assessments		•		•	•		•	•	•
Hurley Stage	8.2.1	X	X					X	X
AN count (HiSCR)	8.2.2	X	X	X	X	X	X	X	X
Modified Sartorius score	8.2.3		X					X	X
Record rescue lesional treatment	8.2.4			X	X	X	X	X	X
HS Pain NRS ^e	8.2.5	X	X	X	X	X	X	X	X
Analgesic use	8.2.6	X	X	X	X	X	X	X	X
HS-PGIC	8.2.7			X	X	X	X	X	X
DLQI	8.2.8	X	X	X	X	X	X	X	X
Optional photography (target area)	8.2.9		X			X		X	

Table 3: Schedule of Assessments (Continued)

2. INTRODUCTION

INCB054707 is a JAK1 inhibitor. Janus kinase signaling regulates many different proinflammatory signaling pathways and is now well-recognized as a key driver for numerous inflammatory skin diseases.

2.1. Background

2.1.1. Hidradenitis Suppurativa

Hidradenitis suppurativa is a chronic disease characterized by recurrent, painful, deep-seated, rounded nodules and abscesses of apocrine gland-bearing skin. Abscesses typically rupture and release purulent drainage. Abscesses and nodules may heal with scarring and the formation of fistulas or sinus tracts (Revuz 2009). Thus, many patients with HS develop permanent sequelae of past inflammation that are only remediable through surgical excision of the involved skin areas. Onset is usually after puberty, although it is most common during the third decade of life and may persist in old age. The prevalence rate is about 1% (range: 0.2%-4%; Jemec et al 1996, Revuz et al 2008). Axillary and inguinal involvement is more common in females; perianal and buttocks localizations are prevalent in males. Genetic susceptibility, smoking, and obesity are important risk factors for the development of HS. An association between HS and metabolic syndrome has recently been established (Miller et al 2014).

Hidradenitis suppurativa significantly affects healthcare costs and health-related quality of life. A recent study indicates that HS imposes a greater negative impact on quality of life than does psoriasis (Hamzavi et al 2017). Rare complications of HS include fistula formation into the urethra, bladder, rectum, or peritoneum; lymphedema of the limbs or scrotal elephantiasis; and squamous cell carcinomas of the skin originating from HS lesions.

The pathogenesis of HS has not yet been fully elucidated. It has been suggested that follicular plugging followed by the release of follicular material into the dermis are primary events that activate the immune system. Defects in host defense mechanisms as well as innate and adaptive immunity may also contribute. Unravelling which cytokines are involved has been the main objective of several studies. Recently, it has been shown that the IL-23/Th17 and IL-12/Th1 pathways are expressed in HS skin (Schlapbach et al 2011). Although TNF-α presents in inflammatory HS skin, several studies indicate that it may not be one of the key contributors in the pathogenesis of this disease (Kelly et al 2015, van der Zee et al 2012, Moran et al 2017), suggesting opportunities for other potential therapeutic targets.

2.1.2. Current Treatment and Unmet Need in Hidradenitis Suppurativa

[figure not shown]
Treatment of HS depends on the extent and activity of disease. Current European guidelines for the treatment of HS generally recommend topical clindamycin or oral tetracycline as first-line therapy for mild disease (Gulliver et al 2016, Zouboulis et al 2015). For moderate to severe disease, oral clindamycin and rifampin combination therapy are used as first-line treatment, and adalimumab (TNF- α inhibitor) is used as a second-line treatment. Of note, the latter is the only

US FDA-approved systemic therapy for HS. In more severe cases with extensive scarring, surgical intervention is used to remove the nondynamic components of HS (eg, scarring, fistulas, and sinus tracts) that are not expected to respond to drug therapy. These comprise a number of surgical procedures (eg, incision and drainage, de-roofing, and excision) laser (Nd:YAG) and radiation therapy (Jemec 2012). Other systemic/pharmacologic therapies include drugs such as acitretin, isotretinoin, dapsone, antiandrogens (in female patients), intralesional injections of triamcinolone, and a number of TNF-α inhibitors (Rambhatla et al 2012).

Given that the current pharmacologic treatments are moderately effective at best, are not approved for HS (except for adalimumab), and are often associated with significant side effects, there is a need for new effective agents for the treatment of HS. Although several biologic agents are undergoing clinical investigation at this time (IL-17 inhibitors: bimekizumab and secukinumab), an oral treatment with a JAK1-inhibitor such as INCB054707 has the potential to address an unmet medical need for patients with HS.

2.1.3. JAK-STAT Signaling in Inflammatory Skin Disease

The JAK family of kinases includes JAK1, JAK2, JAK3, and TYK2. The JAK-STAT pathway is used by cytokines including ILs, interferons, and other molecules to transmit signals from the cell membrane to the nucleus. Upon engagement of extracellular ligands, intracellular JAK proteins, which associate with type I/II cytokine receptors, become activated and phosphorylate STAT proteins, which dimerize and then translocate into the nucleus to directly regulate gene expression. Among all JAK family members, JAK1 signaling relates primarily to cytokines involved in inflammation (Rawlings et al 2004).

To date in dermatology, psoriasis has been the most heavily studied indication for JAK inhibitors including tofacitinib, baricitinib, and ruxolitinib. The sponsor has completed 4 clinical studies with JAK1 and JAK2 inhibitors for the treatment of psoriasis. Both topical ruxolitinib (Punwani et al 2015) and oral INCB039110 (Bissonnette et al 2013) have been associated with clinical improvement and benefit in patients with chronic plaque psoriasis.

2.1.4. INCB054707

INCB054707 potently inhibits JAK1 with approximately 45- to > 1000-fold selectivity over other JAK family members (ie, JAK2, JAK3, and TYK2). It is highly selective in that it does not significantly inhibit a broad panel of other kinases. INCB054707 is being developed for oral administration, a route of administration that is widely used and helps promote patient compliance with medication dose administration. Preclinical *in vitro* results indicate that INCB054707 inhibits T-cell proliferation and production of proinflammatory cytokines (eg, IL-17). *In vivo*, INCB054707 is efficacious in animal models of rheumatoid arthritis and psoriasis.

2.2. Study Rationale

Given that TNF- α may not be the major driver for HS pathogenesis, and that there is a relatively high number of patients who do not sufficiently respond to therapy with the only approved HS medication impacting that pathway (adalimumab, a TNF- α inhibitor), there remains a significant unmet need for new treatments for HS.

2.2.1. Scientific Rationale for Study Design

Recent literature suggests that the main cytokines involved in HS pathogenesis are IL-1β, IL-17, IL-23, IL-10, and, to a lesser extent, TNF-α (Kelly and Prens 2016). The expression and/or activity of these cytokines is mediated at the intracellular level through JAK-STAT signaling, and primarily JAK1 inhibition (see Section 2.1.3).

In the current study, the clinical safety and efficacy of 15 mg QD INCB054707 will be evaluated in adult participants with moderate to severe HS. The primary endpoint is to evaluate the safety and tolerability of INCB054707.

For participants experiencing bothersome symptoms related to either rapid abscess formation or secondary infection at the diseased sites, appropriate rescue treatments will be offered to immediately evacuate pus (incision and drainage), alleviate the level of inflammation (intralesional triamcinolone), or control infection (see Sections 6.6.2 and 8.2.4)

It is expected that the outcome of this study will be instrumental in informing the dose-ranging Phase 2b study.

2.2.2. Justification of Dose

This study will evaluate up to 8 weeks of oral self-administration of INCB054707 15 mg QD. The selected dose is within a dose range previously shown to be safe and well-tolerated in 10 days of administration in healthy participants as well as within the estimated safety margins using the exposures at the no-observed-adverse-effect-levels from the 6-month toxicity study in the rat and the 9-month toxicity study in the dog. Approximately 10 participants with moderate to severe HS will be enrolled.

2.3.2. Clinical Studies

In 2 healthy volunteer studies with single doses of INCB054707 up to 405 mg, multiple doses of INCB054707 up to 120 mg, or placebo for up to 10 days, mild to moderate headaches were reported in up to 31% of participants in the multiple-dose study. The events resolved spontaneously following discontinuation of INCB054707.

2.3.3. Benefit Assessment

Participants may experience clinically meaningful improvements in their HS lesions during the study and may additionally benefit from the comprehensive safety assessments conducted as part of the study (eg, clinical laboratory tests, physical examinations, ECGs).

They will also contribute to the process of developing a novel anti-inflammatory agent for HS, a disease with high unmet need that is severely debilitating to participants' well-being and daily functioning.

2.3.4. Benefit-Risk Conclusion

Taking into account the safety measures taken to minimize risk to participants in this study, the potential risks identified in association with INCB054707 are justifiable and appropriately balanced by the anticipated efficacy benefits expected to be afforded to this specific group of participants and, more broadly, to the general population of patients with HS. More detailed information about the known and expected benefits and risks and reasonably expected adverse events of INCB054707 may be found in the IB.

3. OBJECTIVES AND ENDPOINTS

Table 5 presents the objectives and endpoints.

Table 5: Objectives and Endpoints

Objectives	Endpoints	
Primary		
To evaluate the safety and tolerability of INCB054707.	• Frequency, duration, and severity of AEs, clinical laboratory test results, vital signs results, ECGs, and physical examination findings	
Secondary		
To evaluate the systemic exposure to INCB054707.	Population PK parameters of INCB054707.	
To evaluate the efficacy of INCB054707.	Proportion of participants with a HiSCR at each visit.	
	• Proportion of participants achieving an AN count of 0 to 2 at each visit.	
	Mean change from baseline in the HS Pain NRS scores, worst and average pain, at each visit.	
	Mean change from baseline to Week 8 in the modified Sartorius scale score.	
	Mean change from baseline in the number of draining fistulas count at each visit.	
	• Proportion of participants at each category of Hurley Stage at baseline and Week 8.	
	Proportion of participants with change from baseline in Hurley Stage at Week 8	
	• Proportions of participants in each HS-PGIC category during the treatment period.	
To assess the need for rescue lesional treatment.	Proportion of participants requiring rescue lesional treatment.	
	Number of interventions with rescue lesional treatment.	
To assess patient-reported quality of life burden.	Proportion of participants at each scoring category of DLQI at each visit.	

Table 5: Objectives and Endpoints (Continued)

4. STUDY DESIGN

4.1. Overall Design

This is a Phase 2, multicenter, open-label, single-arm study to assess the safety of 15 mg QD INCB054707 over 8 weeks in men and women aged 18 to 75 years with moderate to severe HS with a targeted enrollment of up to 10 participants.

Safety assessments include monitoring of AEs, clinical laboratory tests, vital signs, ECGs, and physical examinations.

Efficacy assessments include HiSCR as assessed by the AN count, HS Pain NRS, modified Sartorius scale, draining fistula count, and need for rescue lesional treatment. Quality of life will be assessed using the DLQI (participant-reported).

Optional medical photographs of a target lesion will be taken at selected anatomic sites to illustrate the outcome of the study.

4.2. Overall Study Duration

The study will consist of a screening period of up to 28 days, an 8-week open-label, single-arm treatment period, and a 4-week safety follow-up period. The estimated total duration of study participation is approximately 16 weeks for each participant.

4.3. Study Termination

The investigator retains the right to terminate study participation at any time, according to the terms specified in the study contract. The investigator is to notify the IRB/IEC in writing of the study's completion or early termination, send a copy of the notification to the sponsor or sponsor's designee, and retain 1 copy for the site study regulatory file.

The sponsor may terminate the study electively or if required by regulatory decision. If the study is terminated prematurely, the sponsor or designee will notify the investigators, the IRBs/IECs, and regulatory bodies of the decision and reason for termination of the study.

5. STUDY POPULATION

Deviations from eligibility criteria are not allowed because they can potentially jeopardize the scientific integrity of the study, regulatory acceptability, and/or participant safety. Therefore, adherence to the criteria as specified in the Protocol is essential. Prospective approval of Protocol deviations to recruitment and enrollment criteria, also known as Protocol waivers or exemptions, are not permitted.

5.1. Inclusion Criteria

Participants are eligible to be included in the study only if all of the following criteria apply:

- 1. Men and women aged 18 to 75 years at the time of consent.
- 2. Diagnosis of HS (confirmed by a dermatologist) with a disease duration of at least 6 months before screening.
- 3. Stable course of HS for at least 90 days before screening, as determined by the investigator.
- 4. HS lesions present in at least 2 distinct anatomic areas, 1 of which must be Hurley Stage II (ie, recurrent abscessed with tract formation and cicatrization; single or multiple, widely separated lesions) or Hurley Stage III (ie, diffuse, or near diffuse involvement or multiple interconnected tracts and abscesses across the entire area) at screening and baseline.
- 5. Total AN count of at least 3 at screening and baseline.
- 6. Willingness to avoid pregnancy or fathering children based on the criteria below:
 - a. Male participants must agree to take appropriate precautions to avoid pregnancy (with at least 99% certainty) from screening through 90 days after the last dose of study drug. Male participants must also refrain from donating sperm during this period. Permitted methods that are at least 99% effective in preventing pregnancy (see Appendix A) should be communicated to the participant and his understanding confirmed.
 - b. Women of childbearing potential must have a negative serum pregnancy test at screening and a negative urine pregnancy test before the first dose on Day 1 and must agree to take appropriate precautions to avoid pregnancy (with at least 99% certainty) from screening through safety follow-up. Permitted methods that are at least 99% effective in preventing pregnancy (see Appendix A) should be communicated to the participants and their understanding confirmed.
 - c. Women of nonchildbearing potential (ie, surgically sterile [hysterectomy, bilateral oophorectomy, or bilateral salpingectomy] OR postmenopausal, defined as ≥ 12 months of amenorrhea before screening without an alternative medical cause, confirmed by FSH levels at screening) are eligible.

5.2. Exclusion Criteria

Participants are excluded from the study if any of the following criteria apply:

- 1. Women who are currently pregnant or lactating.
- 2. Presence of > 20 draining fistulas at screening and baseline.
- 3. Participants with concurrent conditions or history of other diseases, as follows:
 - a. Any clinically significant medical condition other than HS, as determined by the investigator, that is not adequately controlled with appropriate treatment.
 - b. Any other active skin disease or condition (eg, bacterial, fungal, or viral infection) that may interfere with the course, severity, or assessments of HS.
 - c. Active systemic viral infection or any active viral infection that, based on the investigator's clinical assessment, make the participant an unsuitable candidate for the study.
 - d. Current herpes zoster infection, a history of recurrent herpes zoster, a history of disseminated herpes simplex, or a history of herpes zoster.
 - e. History of malignancy, including lymphoma and leukemia within 5 years before baseline, other than a successfully treated nonmetastatic cutaneous squamous cell carcinoma, basal cell carcinoma, or localized carcinoma *in situ* of the cervix.
 - f. Albinism.
- 4. Prolonged QT interval corrected for heart rate using Fridericia's formula (QTcF), defined as ≥ 450 msec.

Note: Prolonged QTcF values of \geq 450 msec at screening are to be confirmed by performing 2 additional ECGs and averaging the results to determine if the averaged value meets the exclusion criterion.

5. Positive test result for TB from the QuantiFERON-TB Gold test, or equivalent, at screening (or, if 2 indeterminate tests or not available, then as evaluated by a purified protein derivative test with a result of < 5 mm of induration within 3 months of screening) or a history of active TB.

Note: If the participant has possible evidence of a latent TB infection, the participant must have documented completion of an adequate course of therapy for latent TB and provide recent (within 3 months) posteroanterior and lateral views chest x-ray without changes suggestive of active or latent TB, prior to baseline.

- 6. Positive serology test results for HIV, HBsAg, HBV core antibody, or HCV (HCV-antibody with positive HCV-RNA) at screening.
- 7. Decreased blood cell counts at screening, defined as follows:
 - a. Leukocytes $< 3.0 \times 10^9/L$ ($< 2.5 \times 10^9/L$ for participants who are African-American).
 - b. ANC $< 1.5 \times 10^9 / L$.
 - c. Lymphocytes $< 0.8 \times 10^9/L$.
 - d. Hemoglobin < 10 g/dL.
 - e. Platelets $< 150 \times 10^9/L$.

- 8. Severely impaired liver function (Child-Pugh Class C) or ALT or AST levels $\geq 1.5 \times \text{ULN}$.
- 9. Impaired renal function with serum creatinine > 1.5 mg/dL.
- 10. Use of the following medications:
 - a. Previous use of JAK inhibitors, systemic or topical (eg, ruxolitinib, tofacitinib, baricitinib, filgotinib, lestaurtinib, and pacritinib).

Version 1

- b. Previous use of adalimumab or any other TNF-α treatment, investigational, or any experimental treatments within 12 weeks or 5 half-lives (whichever is longer) before baseline.
- c. Systemic immunosuppressive or immunomodulating drugs (eg, oral or injectable corticosteroids, methotrexate, cyclosporine, and azathioprine) within 4 weeks or 5 half-lives (whichever is longer) before baseline.
- d. Other systemic therapies for HS (eg, retinoids and antiandrogens) with potential therapeutic impact for HS within 4 weeks or 5 half-lives (whichever is longer) before baseline.
- e. Surgical, laser, or IPL intervention in area with HS lesion within 4 weeks before baseline.
- f. Systemic anti-infectives (eg, antibiotics, antivirals, antifungals) within 4 weeks or topical anti-infectives on HS lesions (eg, antibiotics, antivirals, antifungals) within 2 weeks before baseline.
- g. Received live vaccine within 6 weeks before baseline or planning to receive live vaccine during the course of the study or within 6 weeks after EOT.
- h. Topical antiseptic washes, creams, soaps, ointments, gels, and liquids containing antibacterial agents to treat HS, except those listed in Sections 6.6.2.3 and 6.6.2.4, within 2 weeks before baseline.
- Potent systemic CYP3A4 inhibitors and inducers (see Appendix B) or fluconazole within 2 weeks or 5 half-lives (whichever is longer) before baseline.
 Note: Topical agents with limited systemic availability are permitted.
- 11. Known or suspected allergy to INCB054707 or any component of the study drug.
- 12. Known history of clinically significant drug or alcohol abuse in the last year prior to baseline.

14. Inability or unlikeliness of the participant to comply with the dose schedule and study evaluations, in the opinion of the investigator.

- 15. Any condition that would, in the investigator's judgment, interfere with full participation in the study, including administration of study drug and attending required study visits; pose a significant risk to the participant; or interfere with interpretation of study data.
- 16. Inability of the participant (or parent, guardian, or legally authorized representative) to comprehend or unwilling to sign the ICF.

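### Exclusion criterion 5 states its PPD fallback the wrong way round: induration under 5 mm, the negative result, is given as the one that excludes

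*Protocol*

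**What the plan says.** Section 5.2 of the protocol opens: "Participants are excluded from the study if any of the following criteria apply". Criterion 5 starts with "Positive test result for TB from the QuantiFERON-TB Gold test, or equivalent, at screening". A parenthesis then covers the case where two tests are indeterminate or no test is available: "then as evaluated by a purified protein derivative test with a result of < 5 mm of induration within 3 months of screening". A history of active TB also excludes.

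A Note on latent infection follows: "If the participant has possible evidence of a latent TB infection, the participant must have documented completion of an adequate course of therapy". The participant must also "provide recent (within 3 months) posteroanterior and lateral views chest x-ray without changes suggestive of active or latent TB, prior to baseline".

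The opening of Section 5 requires sites to keep to the criteria as the protocol states them, and it rules out waivers. No other PPD cut-off appears in the visible protocol or SAP. Protocol Section 8.3.5.2 refers sites to the Laboratory Manual and Section 8.3.5.1 refers to Table 10; neither is visible in the public documents.

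**The concern.** In an exclusion list, a stated value is the value that removes a participant. Criterion 5 announces a positive TB test as the reason for removal and then, for the skin test, supplies the size of reaction that counts as negative. The two limbs of one sentence therefore point in opposite directions.

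This is a safety threshold in a trial of an oral JAK1 inhibitor, which Protocol Section 2.1.4 says inhibits T-cell proliferation and cytokine production in vitro. The eligibility wording must be followed as printed and no waiver can be granted, so the sentence should say what is meant. A site that followed the sign literally would turn away a non-reactor, and for a reactor it would have to rely on the Note or on judgment.

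**Working it through.** The plan states no figure to reproduce here. The check is one of logic, plus a count of comparable thresholds.

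**Step 1. Direction of each limb** (Section 5.2 lead-in and criterion 5, before the Note is applied):

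| Screening result | Effect as printed | Effect if the limb follows the word *positive* |
|---|---|---|
| QuantiFERON positive | Excluded | Excluded |
| QuantiFERON negative | Not excluded | Not excluded |
| Fallback PPD < 5 mm | Excluded | Not excluded |
| Fallback PPD >= 5 mm | Not excluded by this limb | Excluded |

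The first two rows agree. The last two are reversed, and changing the sign makes all four agree.

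**Step 2. Comparison with the other thresholds in Section 5.2.** Counting visible thresholds on a measured result and leaving out washout and other time windows:

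1. Draining fistulas: "Presence of > 20 draining fistulas at screening and baseline"
2. QTcF >= 450 msec
3. Leukocytes < 3.0 × 10⁹/L (< 2.5 for African-American participants)
4. ANC < 1.5 × 10⁹/L
5. Lymphocytes < 0.8 × 10⁹/L
6. Hemoglobin: "Hemoglobin < 10 g/dL"
7. Platelets < 150 × 10⁹/L
8. ALT or AST >= 1.5 × ULN
9. Creatinine: "Impaired renal function with serum creatinine > 1.5 mg/dL"
10. PPD < 5 mm

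Items 1 to 9 all give the abnormal, excluding value (9 of 9). Item 10 gives the acceptable value, so 1 of 10 is inverted. The section's own convention is to state the excluding value, and the PPD clause departs from it.

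**Step 3. Size.** The expected number misclassified would be

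number screened × share reaching the fallback × share of those with the PPD result in question.

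None of the three factors is in the documents. The planned figure of about 10 is the number enrolled, whereas an exclusion acts on those screened, so it cannot stand in for the first factor. I therefore give no estimate.

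**Step 4. What limits the effect.**

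- QuantiFERON is among the study's laboratory tests (SAP Section 8.3.2), and laboratory tests are done centrally with narrow exceptions (SAP Section 8.3.1). The fallback should therefore be uncommon.
- The Note is mandatory wherever latent TB is possible.
- Criterion 15 lets the investigator exclude anyone at significant risk.
- The full analysis set is every enrolled participant with at least 1 dose (SAP Section 5.3.1), so it does not depend on criterion 5.

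**The case against.** **The sign may have been misread from the PDF.** The point rests on one character, and the extracted text does contain character errors, for example in a page header in the contents pages. Nine sensible signs elsewhere show that this one is odd; they do not by themselves separate an author's slip from a reading error. Still, the other signs in Section 5.2 came through sensibly, including both directions and the *or equal* forms, and a less-than sign misread from less-than-or-equal would still be inverted. A misread is possible but unlikely. What stands is that the source document should be checked first.

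**Sites will understand what is meant.** Probably so, because the opening word of the criterion shows the intent. The Laboratory Manual or Table 10 may also carry a correct cut-off, and nothing here shows that sites lacked one. That lowers the practical effect but does not correct the protocol sentence.

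**The Note and criterion 15 already protect participants.** Largely true, and the main reason to call the effect small. The Note, however, turns on possible evidence of latent infection, which the visible text does not define.

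**Stronger readings a reader might infer.**

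- *Enrolling a non-reactor is a protocol violation that will appear in the SAP's deviation listings.* The documents do not support this. A result under 5 mm is not a positive result, so the sentence contradicts itself rather than clearly defining a violation, and nothing visible suggests that a site would record one.
- *One of the two errors, turning away a non-reactor or admitting a reactor, is the more frequent.* The rates needed to rank them are not given.

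**Conclusion.** Criterion 5 is wrong as written. Its PPD limb names the negative result as the excluding one and contradicts the QuantiFERON limb beside it. It should be corrected because it is an operative safety threshold that must be applied as printed.

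The effect is small and cannot be put as a number of participants. The judgment that the fallback is uncommon rests on QuantiFERON being a listed study test, not on a stated rate. No sample size, endpoint or analysis set is touched.

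The conclusion assumes that the printed sign matches the source document and that a larger induration is the positive direction of the skin test. Whether 5 mm is the right cut-off is for the sponsor's medical team.

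Two further inferences should be resisted. The text does not show that the trial would admit people with untreated TB infection, given the Note and criterion 15. Nor does it settle whether a treated participant who meets the Note may enter despite a positive test. That is a separate question, and it applies to QuantiFERON and PPD alike.

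**What to change.** 1. Check the inequality sign in criterion 5 against the source document.
2. If it is as printed, change the parenthesis to >= 5 mm of induration, with the cut-off confirmed by the sponsor's medical team. Alternatively, take < 5 mm out of the criterion and state it in a note as the acceptable negative result.
3. Check the eligibility eCRF page and the Laboratory Manual for the same wording.
4. Do not write in an exception for PPD alone. If the sponsor wants to say whether the Note overrides a positive test, it should decide this once and apply it to both tests; otherwise treated PPD reactors could be handled differently from QuantiFERON-positive participants.

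The cost is a one-line amendment with IRB/IEC approval (Protocol Section 11.1) and the two document checks. Sample size, visit schedule and analysis sets stay as they are.
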